#### Study Arm 2: Community Linkage-To Care Arm (Control Condition) Procedures:

Participants allocated to the community linkage-to-care arm will complete screening, be offered enrollment, and undergo informed consent as in the telemedicine arm. Following study inclusion and enrollment, research staff will refer the participant to a local community health clinic to engage in hepatitis C care and seek treatment. Peers will assist patients to engage with local primary care and health plan resources and will receive an information sheet on optional clinics to attend and questions to ask their provider. TAU participants will be encouraged to take this to their visit. Research assistants will outreach to participants regularly to determine if they have engaged in local health resources and schedule assessment visits. A bidirectional release of information will be requested. The study clinical pharmacist or research assistant will assess adherence medication adherence at week 4 and end of treatment via telephone. SVR12 laboratory testing will be performed by the community provider with at least one telephone reminder prior to lab due date. 12 weeks post end of treatment study assessments will coincide with SVR12 lab results visit and 36 week post end of treatment assessments performed as in the telemedicine arm.

Chart abstraction for participants in both arms will be performed in order to assess the number of and types of interactions the peers have with participants.

In either arm, participants who do not initiate treatment by 12 weeks after randomization will begin their assessment timeline, mirroring treatment timeline for an 8-week direct acting antiviral regimen. For these participants, the study research assistant will collect study assessments at week 16 (corresponding to 4-week post-treatment initiation), week 20-22 (corresponding to end of treatment visit), week 32 (corresponding to 12 weeks post-treatment visit), and week 56 (corresponding to 36

weeks post-treatment visit) after randomization; the primary study outcome will be assessed at 32 weeks after randomization.

Participant Assessments:

Phase 1:

- Blood draw and DBS specimen collection for HCV RNA and Hepatitis B core antibody

Phase 2:

Assessment/Activity	Pre-Screen	Screen	Baseline (Week 0)	4-Week after treatment initiation	End of Treatment	12-week Post-Treatment	***36-Week Post Treatment Completion	As Needed

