Pre-Screening Survey	X							
Demographics		X						
Inclusion/Exclusion		X						
Rapid HCV Test	X							
CPT Assessment		X						
Participant Survey								
Medical Care History			X		X	X	***X	
Barriers to treatment			X		X	x	***X	
Engagement with Harm Reduction & Substance Use Treatment			X	X	X	X	***X	
Substance Use			X	X	X	X	***X	
Perceived Stigma of Drug Use			X	X	X	X	***X	
HCV Treatment History			X		X			
HCV Treatment Completion					X			
HCV Treatment Adherence				X	X			
Treatment Satisfaction					X			
Experience with Telemedicine					**X			
Experience with Peer Support Specialist					**X			
Blood Draw/ Medical Procedures								
HCV RNA		X				X		
Hepatitis B Sag		X						
Hepatitis B SAg		X						
Hepatitis B cAb		X						
Hepatitis A Ab		X						
CMP		X				X		

CBC		X				X	
INR/prothrombin		X					
HCV genotype		X					
B-HCG (women<50)		X					
SC Reviews Labs		X				X	
Ultrasound							**X
Telemedicine Visit			**X				
Medication Counseling			**X	**X	X*		
HCV Genotype and Resistance Testing							**X
Chart Abstraction					X	X	
Peer interaction log					X		
HCV treatment provider visits					X		
Administrative							
Written informed consent		X					
Locator Form	X		X	X	X	X	X
Master Enrollment Log			X				
Progress Note Check List	X	X	X	X	X	X	X
Reportable Events Log							X
Adverse Event							X
Inventory Form							X
Visit Compensation Log	X		X	X	X	X	X

\*\*\*X: 36 Week Survey only if participant qualifies

\*\*X: Only Telemedicine Pt.

\*X: Number of weeks of treatment depends on ppt.

Participants complete brief REDCap surveys regarding symptoms, substance use, and harm reduction engagement at baseline, 4 weeks, end of treatment, 12 post end of treatment, and 36 weeks post end of treatment. These surveys will be conducted over the phone or in person.

Participants undergo phlebotomy at screening and 12 post end of treatment.

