#### **Study Measures:**

The primary outcome is sustained viral response at 12 weeks post treatment (SVR12). Secondary outcomes include a) HCV treatment initiation, b) HCV Treatment completion (filled final prescription and self-reported > 90% HCV treatment pills taken), c) engagement with harm reduction resources, d) substance use, e) perceived stigma, and f) engagement in addiction treatment resources. Exploratory endpoints include a) treatment satisfaction with hepatitis C treatment, adapted from the single-item Medication Satisfaction Questionnaire, and b) reinfection vs. virologic relapse/failure.

Adherence to Phone Visits: Adherence to these phone visits is defined as +/- 5 days

Prescreen, baseline and follow-up surveys collected in the field or via phone will first be documented on paper forms. These will then be entered into REDCap by the RA. The source documents will be kept in a locked file cabinet in a secure location.

Qualitative interviews will be recorded on an encrypted recorder and stored on a secure, encrypted computer.

Survey data will be used to determine HCV status of participants with a detectable plasma HCV RNA, which were collected on or after SVR12 timepoint (either 12 weeks after end of treatment for those who initiated treatment or 32 weeks after randomization for those who did not initiate treatment). The primary SVR12 outcome will be sustained viral response 12 weeks after treatment for participants who initiated treatment within 6 months. Participants who did not start treatment within 6 months will be considered treatment failure. Measuring detectable plasma HCV RNA for both participants who initiated and did not initiate within 6 months of randomization will provide a framework to assess for potential biasing impact of spontaneous clearance on assumption of treatment failure for participants who did not initiate treatment within 6 months.

**Probable Relapse/Failure:** Probable virologic relapse or failure is defined as a detectable plasma HCV RNA 12 weeks or more after the end of treatment if a) participant denies any injection drug use, or b) participant injecting drugs but notes 100% adherence to recommendations on Safe injection practices, including use of clean works (cooker, cotton, rinse) with every injection.

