## Data Analysis:

Pre-specified analyses for this study will be intention-to-treat (ITT) comparisons between telemedicine and treatment as usual (local treatment referral) on primary and secondary outcomes. Prior to conducting these analyses, we will compare baseline covariate distributions (demographics, etc.) between randomized groups using standardized mean differences (SMDs) and bivariate statistical tests (e.g. t-tests, Chi-square tests). If a significant imbalance in any variable is noted, i.e., a SMD > 0.25 and  $p < .2$ , we will include that variable as a covariate in future analyses. All primary and secondary analyses will utilize generalized linear (mixed) models (GLMMs) with distributions and link functions appropriate for the distribution of the outcome variable. Fixed effects of interest in the models will be timepoint (baseline, 4 weeks, end of treatment, 12 weeks post-treatment, 36 weeks post-treatment), randomized group (telemedicine vs. TAU), and their interaction. If more than one timepoint is included in the analysis, GLMMs will include person-level random intercepts to account for repeated measurements on subjects. Hypotheses will be tested using between-group comparisons at each timepoint of interest, or within-group comparisons across timepoints.

Hypothesis 1: Participants randomized to receive tele-HCV treatment will have superior SVR-12 rates compared to those randomized to TAU (referral for local treatment).

Analytic strategy: We assess the effect of telemedicine versus TAU on SVR at 12 weeks post-treatment completion using logistic regression. Missing HCV viral load data will be considered non-suppressed in the main ITT analysis. Sensitivity analyses will include a per-protocol analysis and a repeat of the main analysis using multiple imputation of missing data.

Hypothesis 2: Participants randomized to receive tele-HCV treatment will have superior rates of HCV treatment initiation (filled first prescription) compared to those randomized to TAU.

Analytic strategy: We assess the effect of telemedicine versus TAU on treatment initiation by 4 weeks post-baseline using logistic regression. Missing treatment initiation data will be considered non-initiated in the main ITT analysis. Sensitivity analyses will include a per-protocol analysis and a repeat of the main analysis using multiple imputation of missing data.

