Hypothesis 3: Participants randomized to receive tele-HCV treatment will have superior rates of HCV treatment completion (filled final prescription and self-reported > 90% HCV treatment pills taken) compared to those randomized to TAU.

Analytic strategy: We assess the effect of telemedicine versus TAU on treatment completion by 12 weeks post-baseline using logistic regression. Missing treatment completion data will be considered incomplete in the main ITT analysis. Sensitivity analyses will include a per-protocol analysis and a repeat of the main analysis using multiple imputation of missing data.

Hypothesis 4: Participants randomized to receive tele-HCV treatment will have a higher likelihood of engagement with harm reduction resources, lower rates of substance use, lower stigma, and higher engagement in addiction treatment resources compared to those randomized to TAU (referral for local treatment).

Analytic strategy: We assess the effect of telemedicine versus TAU on these outcomes at all post-baseline timepoints using mixed effects regression models. Missing outcome data will be handled using full information maximum likelihood. We will conduct per-protocol analyses as sensitivity analyses.

**Qualitative Evaluation.** Audio-recorded interviews will be professionally transcribed; transcripts will be uploaded into qualitative analysis software (NVivo™). Comagine research staff create a coding scheme, conduct coding, and revise in an iterative process that has been successfully implemented by the study team in other mixed-methods projects. The qualitative data provides complementary information to illuminate and expand quantitative findings, including survey results and measures of treatment initiation and completion.

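### Read literally, Hypothesis 3 counts completion only up to 12 weeks after baseline, which mixes speed of starting with completion and conflicts with the plan's other windows

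*Combined protocol and SAP*

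**What the plan says.** All references are to the combined protocol and SAP.

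- **Data Analysis, Hypothesis 3.** Completion means that the final prescription was filled and more than 90% of pills were taken by self-report. The analysis is: "We assess the effect of telemedicine versus TAU on treatment completion by 12 weeks post-baseline using logistic regression". Missing completion data count as incomplete. The sensitivity analyses are per-protocol and multiple imputation.
- **Data Analysis, Hypothesis 2.** The companion outcome is: "We assess the effect of telemedicine versus TAU on treatment initiation by 4 weeks post-baseline using logistic regression".
- **Study Measures.** Completion is defined in the same way but with no time limit. For the primary outcome: "The primary SVR12 outcome will be sustained viral response 12 weeks after treatment for participants who initiated treatment within 6 months". Later starters and non-starters count as failures. The SVR12 timepoint is "either 12 weeks after end of treatment for those who initiated treatment or 32 weeks after randomization for those who did not initiate treatment".
- **Participant Assessments, Phase 2 schedule.** The row "HCV Treatment Completion" is marked at the end-of-treatment visit only.
- **Study Arm 2 procedures, applying to either arm.** "participants who do not initiate treatment by 12 weeks after randomization will begin their assessment timeline", with visits at "week 16 (corresponding to 4-week post-treatment initiation), week 20-22 (corresponding to end of treatment visit") after randomization.
- **Study Arm 1 procedures.** Most courses last 8 weeks; a small subset lasts 12 weeks.

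**The concern.** Hypothesis 3 claims superior completion rates. A cut-off 12 weeks after baseline leaves little room for an 8-week course to be started and taken, and almost none for a 12-week course. Someone who starts late, takes every pill and is cured is an SVR12 success on the primary outcome and a non-completer on this one.

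At stake is what the test measures. If the arms complete equally but one starts sooner, the literal outcome can show a difference. If the arms differ in completion but start at the same speed, late completers drop out of the count in both arms and the difference shrinks. If telemedicine also starts faster, the difference grows. A faster telemedicine start is plausible, because for most in that arm the assessment visit is also the initiation visit, but the documents give no start times for either arm.

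**Working it through.** **1. The plan's own calendar.** The fixed clock starts at week 12 and mirrors an 8-week course: 12 + 4 = 16, 12 + 8 = 20, 20 + 12 = 32, 20 + 36 = 56. These match the stated visits at weeks 16, 20-22, 32 and 56. Hypothesis 2's limit plus an 8-week course gives 4 + 8 = 12, which is Hypothesis 3's limit.

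**2. Latest start that can count (no assumption about start times).** Baseline and randomization come together, before treatment (Screening Procedures). Latest start = 12 − 0.9 × course length.
- 8-week course: 12 − 7.2 = week 4.8 (whole course: 12 − 8 = week 4).
- 12-week course: 12 − 10.8 = week 1.2 (whole course: 12 − 12 = week 0).

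**3. Two cases.**
- An 8-week course begun at week 6 reaches 90% of pills at 6 + 7.2 = week 13.2 and ends at week 14. Its SVR12 test at week 26 can be a primary success, yet it is not completed under Hypothesis 3.
- A 12-week course begun at week 3 is initiated under Hypothesis 2, but reaches 90% of pills at 3 + 10.8 = week 13.8, so it cannot be completed under Hypothesis 3.

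**4. Share of true completers missed (illustration).** Assumptions, none from the documents: exponential start times cut at 26 weeks, with F(t) = cdf(t)/cdf(26); the same start times for completers as for all starters; 90% on 8-week courses; the Arm 1 course lengths in both arms.
- Literal: missed = 1 − [0.9 F(4.8) + 0.1 F(1.2)].
- Visit label, week-22 reading: starts after week 12 stay on the fixed clock and are read at week 22. An 8-week course counts if begun by 22 − 7.2 = 14.8, and a 12-week course if begun by week 12. Missed = 1 − [0.9 F(14.8) + 0.1 F(12)].
- Visit label, visits anchored to actual end of treatment: 0% missed.

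| Median start (weeks) | 2 | 3 | 4 | 5 | 8 |
|---|---|---|---|---|---|
| Literal, missed | 24% | 37% | 47% | 54% | 65% |
| Week-22 reading, missed | 1% | 3% | 7% | 11% | 20% |

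Example, median 4: literal 1 − (0.9 × 0.571 + 0.1 × 0.190) = 0.467; week-22 reading 1 − (0.9 × 0.933 + 0.1 × 0.885) = 0.071.

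**5. Effect on the test (illustration).** Two-proportion test, two-sided 0.05, 95% of starters completing, 100 per arm. The last figure is a ceiling, since Number of Subjects says up to 200.

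| Scenario | Full window | Literal | Week-22 reading |
|---|---|---|---|
| Uptake 80% v 60%, median 4 weeks in both arms: proportions | 0.76 v 0.57 | 0.405 v 0.304 | 0.706 v 0.529 |
| Power | 82% | 32% | 73% |
| Uptake 70% in both arms, medians 3 v 8 weeks: proportions | 0.665 v 0.665 | 0.418 v 0.235 | 0.643 v 0.531 |
| Chance of p<0.05 | no true difference | 79% | 36% |

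With uptake 80% v 60% and medians 3 v 5 weeks, literal power is 88% (0.478 v 0.265), above the full-window 82%. The window can therefore raise power as well as lower it.

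**The case against.** The best defence is that weeks 4 and 12 are a matched pair. For the majority regimen they describe a prompt start followed by completion of that course, and completion by a fixed time from randomization is a legitimate intention-to-treat endpoint. This stands in part. For 8-week courses the limit is coherent, and the quantity tested is completion by week 12, so it would be wrong to say that it has nothing to do with completion. But the plan does not label it prompt completion, and the pairing fails for 12-week courses, as the week-3 case shows.

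The second defence is that the wording is a slip for a visit label. The schedule and the untimed definition in Study Measures both point that way, and the reading is workable. It also removes most of the problem: few completers are missed, or none, depending on the clock used for starts after week 12. A reader might infer from the Hypothesis 3 sentence that late completers will certainly be miscounted. The documents do not support that; they support only that the window is contradictory and that one reading has this effect.

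The model's timepoint list, "timepoint (baseline, 4 weeks, end of treatment, 12 weeks post-treatment, 36 weeks post-treatment", contains no week 12 after baseline. That is weak evidence either way: Hypothesis 3 is a single logistic regression, and week-12 status could be derived from dated fills.

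The sensitivity analyses are no answer. Neither is stated to change the cut-off, and a late completer is not missing but classified as incomplete.

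**Conclusion.** The point holds for the literal text and should be fixed. The cut-offs of weeks 4.8 and 1.2 follow from the plan's own figures. The conflict with the 6-month rule, the end-of-treatment collection point and the week 20-22 visit is on the page.

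The size is uncertain. Start times, uptake, regimen shares and the completion rate among starters are all assumed. On those assumptions the literal reading misses 24% to 65% of true completers and visit-label readings miss 0% to 20%. That gap is itself the problem: the same data could give quite different completion rates, and the plan does not say which is meant.

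Three stronger inferences are not supported. The primary SVR12 analysis is not affected. The 79% is not a false-positive rate: it is power to detect a real difference in speed under one assumed scenario, and it falls to 36% on the week-22 reading. Nor do the documents show that the window favours telemedicine, since the effect can go either way. Hypothesis 2 is milder: week-4 initiation is a coherent measure of prompt starting, but it does not measure overall initiation.

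**What to change.** Reconcile the Arm 2 assessment clock, the Phase 2 schedule, Study Measures and the Data Analysis text for Hypotheses 2 and 3, and state an anchor and window for each outcome.

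- **Hypothesis 3.** Define it as completion (final prescription filled and more than 90% of pills taken) of a course begun within the initiation window that the team confirms for the primary outcome. Count non-starters as not completed. Read it at the end-of-treatment visit or, for a late starter kept on the fixed clock, at the next existing contact after the course ends.
- **Clock.** State which assessment clock applies to starts after week 12.
- **Week-12 and week-4 figures.** If a week-12 figure is kept, report it separately as prompt completion. Label Hypothesis 2's week-4 outcome as prompt initiation.

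The cost is small. Hypothesis 3 reads out later: with 6 months taken as about 26 weeks, the last 8-week course would end near week 34 and the last 12-week course near week 38. First-fill or start dates must be available for analysis, but the week-12 and 6-month rules already need them. Pharmacist check-ins, the medical record, outreach with the release of information, and chart abstraction are existing sources. No new visit is needed.

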## ■ Privacy, Confidentiality and Data Security

Our study procedures reflect high levels of protection for subjects.

Training will include time for direct communication of specific roles. HIV Alliance oversees PCC hiring, support, and intervention implementation at in participating counties. Study site visits will be a critical aspect of study success. OHSU research staff will visit PCC field sites at least quarterly support implementation and review data collection.

**Data will be stored in a manner intended to preserve patient confidentiality.** Consent forms and all

PHI will be stored in locked cabinets and on password protected, secure computers. Only study team members will have access to data on secured computers. Participant hard-copy survey data will be stored only at study sites in a locked cabinet until study conclusion. Survey data will be identified only with a unique randomly generated identifier. The identifier will be used instead of subject names or medical record numbers and will not contain any part of the 18 HIPAA identifiers. The file linking the unique identifier with the patient's name will be stored in a separate password-protected file on a secure computer at study sites. Only the study site and overall Study Coordinator, and OHSU PI ([name]) will have access to the linked file. Survey data will be entered in the secure OHSU REDCap system by study staff, and study team members. Site and OHSU study staff will have access to the de-identified data in REDCap. No identifiable information will be emailed between investigators. Data are coded before any transfer. De-identified data may be shared following data lock with the national rural opioids initiative data coordinating center at University of Washington.

**Survey data** will be collected using OHSU's instance of REDCap. Access to the database will be limited to OHSU IRB-approved study staff that are approved to contact or interact with participants. REDCap is a secure, customizable, web-based application for building and managing databases (see <https://octri.ohsu.edu/redcap/index.php>). REDCap resides on a server housed in ITG's Advanced Computing Center (ACC) and is maintained by developers in the Oregon Clinical and Translational Research Institute (OCTRI) in accordance with all relevant OHSU policies and guidelines. Additionally, ACC employs a second firewall within the OHSU network to attain a high level of security and access control. In situations when a secure WiFi connection is not available for REDCap data collection, REDCap Mobile App will be used as an offline data collection means until a WiFi connection is available to securely transmit data to the main REDCap database. REDCap Mobile App database is encrypted on the mobile device's hard drive using SQLCipher to prevent someone from breaking into the file in the event of a stolen device. The REDCap Mobile App will be used on an encrypted laptop/tablet purchased through ITG. REDCap Mobile App with reviewed and approved by ITG Security Engineering group prior to implementation. As a back-up, we may need to collect data using paper surveys and then entering data into REDCap when an internet connection becomes available. If paper surveys are used, those files will be held in a locked case, and stored in locked cabinet in a locked office to securely handle these data.

**Qualitative Data.** Interviews will be digitally audio-recorded and professionally transcribed and transcripts will be uploaded into qualitative analysis software (NVivo) by Comagine study team members. Recordings will be destroyed following analysis. Qualitative interview data will be stored at Comagine on secure servers in password-protected files, accessible only to researchers and subject to Comagine's policy on safeguarding electronic data. Study documents and audio recordings will not contain any identifiable information, but instead will be assigned a unique study identifier. The list linking participants to their unique identifier will be password-protected and maintained within the study's secure REDCap database.

**All study personnel will complete on-line training** in appropriate conduct of research through the OHSU IRB, or equivalent training. The Institutional Review Board of Oregon Health & Science University has policies in place that meet the requirements of 45 CFR 46, Subpart C. The Board

reviews all protocols that involve prisoners; does not permit waivers of consent for subjects who are prisoners; requires OHRP certification once IRB approval is granted; and includes a prisoner representative on the Board during consideration of prison-related proposals, continuing reviews, and amendments. The research protocol will also adhere to the federal policies for protection for children involved as subjects in research (45 CFR 46, Subpart D). The proposed research complies with the Additional Protocol Requirements of 45 CFR 46, Subpart A. The research will be on a condition (substance use disorder) that particularly affects children age 13-21.

